8.2 Baseline Visit (Week 0)

Subjects qualifying for this study will have the following procedures performed/recorded prior to study medication administration:

- Review of inclusion/exclusion criteria (The qualifying CRP levels from the Screening Period will be used for the inclusion criteria review at Baseline.)
- Vital signs (pulse rate, systolic and diastolic blood pressures, temperature and respiration rates)
- Blood samples will be collected for hematology, biochemistry analyses, serum calprotectin, and CRP
- Urine will be collected for urinalysis and for a urine pregnancy test for women of childbearing potential
- Physical examination (including extra-articular assessments, height, and weight)
- TB questionnaire

- BASMI and spinal mobility
- BASDAI
- BASFI
- SF-36
- ASQoL
- EQ-5D
- MASES
- Total spinal pain NRS and nocturnal spinal pain NRS
- Swollen and tender joint counts
- PtGADA
- PhGADA
- WPS
- Resources utilization
- IBD-Q
- Plasma sample for CZP concentration, ADAb
- Plasma sample for biomarkers, if applicable
- Genetics/epigenetics, proteomics if applicable
- Stool sample provided by the subject for fecal calprotectin evaluation
- Prior medications
- AEs
- Contact IXRS to randomize subject and to obtain kit number
- Study drug administration (after all other visit assessments are completed and laboratory samples are drawn)

8.3 Weeks 2 to 96/WD onsite visits

8.3.1 Weeks 2, 4, 12, 24, 32, 36, 48, 52, 60, 72, 84, and 96/WD (\pm 3 Days)

Assessments at these onsite visits include:

- Vital signs: pulse rate, systolic and diastolic blood pressures, temperature will be measured (all visits). If a subject experiences an AE, respiration rate will be measured in addition.
- Blood samples will be collected for hematology and biochemistry analyses (at Weeks 12, 24, 32, 36, 60, 72, 84, and at Week 96/WD), and CRP (at Weeks 2, 4, 12, 24, 32, 36, and from Week 52 onwards every 4 weeks only).
- Urine pregnancy testing for women of childbearing potential will be at Week 96/WD only.

- Urine will be collected for urinalysis (at Weeks 12, 24, 32, 36, 48, 60, 72, 84, and at Week 96/WD).
- Physical examination (at Weeks 12, 24, 36, 48, 60, 72, 84, and at Week 96/WD), including weight at Week 48 and at Week 96/WD.
- Extra-articular assessments (at Weeks 4, 12, 24, 36, 48, 52, 60, 72, 84, and at Week 96/WD).
- TB test (at Week 48 and at Week 96/WD only).
- TB questionnaire (at Weeks 12, 24, 36, 48, 60, 72, 84, and at Week 96/WD).
- MRI (at Week 48 and at Week 96/WD only).
- BASMI and spinal mobility (at Weeks 2, 4, 12, 24, 36, 48, 52, 60, 72, 84, and at Week 96/WD only).
- BASDAI (at Weeks 2, 4, 12, 24, 32, 36, 52, 60, 72, 84, and at Week 96/WD).
- BASFI (at Weeks 2, 4, 12, 24, 36, 60, 72, 84, and at Week 96/WD only).
- SF-36 (at Weeks 4, 12, 24, 36, 60, 72, 84, and at Week 96/WD only).
- ASQoL (at Weeks 2, 4, 12, 24, 36, 60, 72, 84, and at Week 96/WD only).
- EQ-5D (at Weeks 12, 24, 36, 60, 72, 84, and at Week 96/WD only).
- IBD-Q (at Week 96/WD only).
- MASES (at Weeks 12, 24, 36, 48, 60, 72, 84, and at Week 96/WD only).
- Total spinal pain NRS and nocturnal spinal pain NRS (at Weeks 2, 4, 12, 24, 36, 52, 60, 72, 84, and at Week 96/WD only).
- Swollen and tender joint counts (at Weeks 2, 4, 12, 24, 36, 48, 52, 60, 72, 84, and at Completion at Week 96/WD only).
- PtGADA (at Weeks 2, 4, 12, 24, 32, 36, and from Week 52 onwards every 4 weeks only).
- PhGADA (at Weeks 12, 24, 36, 48, 52, 60, 72, 84, and at Week 96/WD only).
- WPS (at Weeks 4, 12, 24, 36, 48, 60, 72, 84, and at Week 96/WD only).
- Resource utilization (at Weeks 12, 24, 36, 48, 60, 72, 84, and at Week 96/WD only).
- Plasma for CZP concentration and ADAb (at Weeks 4, 12, 24, 60, 72, 84, and at Week 96/WD only).
- Plasma for biomarkers (at Weeks 4, 12, 24, 60, 72, 84, and at Week 96/WD only), if applicable.
- Genomics and proteomics (at Weeks 12, 24, 72, and at Week 96/WD only), if applicable.
- Stool sample will be collected for fecal calprotectin at Week 48 and at Week 96/WD only.
- Blood sample will be collected for serum calprotectin at Week 12, Week 24, Week 72 and Week 96/WD only.
- Concomitant medication

- AEs
- Contact IXRS to obtain next kit numbers.
- Study drug administration (after all other visit assessments are completed and laboratory samples are drawn) (all visits except at Week 96/WD).
- Randomization at Week 48
- Check of sustained remission criteria (all visits except Weeks 2, 4, and Week 96/WD visit)

8.3.2 3 to 5 days prior to Week 48

- Blood samples will be collected for hematology and biochemistry analyses and CRP
- BASDAI
- BASFI
- SF-36
- ASQoL
- EQ-5D
- IBD-Q
- Total spinal pain NRS and nocturnal spinal pain NRS
- PtGADA
- Plasma for CZP concentration and ADAbs
- Plasma for biomarkers
- Genetics
- Blood sample will be collected for serum calprotectin
- AEs

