3 STUDY OBJECTIVES

The following key definitions are provided as a reference for understanding the study objectives and are used throughout the protocol.

Sustained remission is achieved when a subject has an ASDAS <1.3 at Week 32 or Week 36 (if ASDAS <1.3 at Week 32, it must be <2.1 at Week 36 [or vice versa]) and at Week 48. A subject is eligible for Part B of the study only if sustained remission is achieved in Part A.

A flare occurs when a subject has an ASDAS ≥ 2.1 at 2 consecutive visits or ASDAS >3.5 at any visit during Part B.

Subjects who meet the criteria of flare during Part B and who crossed-over to full-dose treatment (CZP 200mg Q2W) are regarded as escapers.

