5.1.1 Part A

Period 1 (Screening Period): Up to 5 Weeks before Baseline

Eligible subjects will be informed about the study and sign the informed consent. Concomitant medications such as MTX, SSZ, hydroxychloroquine (HCQ), NSAIDs, and corticosteroids, will be verified and, if required, the washout of any medications not permitted for use during the study will be started. Concomitant medications must follow the protocol requirements in [Table 6.1](#). Subjects will receive a physical examination and vital signs measurements will be

taken. Women of childbearing age will be tested for pregnancy. Laboratory data (hematology, urine, and biochemistry tests) and treatment of latent TB (LTB), where necessary, will be collected. Subjects must undergo a TB test and complete a TB questionnaire. Patient's Global Assessment of Disease Activity, BASDAI, BASMI, spinal mobility assessments, and MRI will be performed. Additionally, a central reading of the x-ray will define the stratification of the subjects into the nr-axSpA or the AS subpopulation.

Period 2 (Open-Label Period): Week 0 (Baseline) to Week 48

Eligible subjects will receive 3 loading doses of CZP sc 400mg at Weeks 0, 2, and 4 followed by CZP 200mg Q2W.

All subjects will be trained on self-administration at Weeks 2 and 4. Subjects will self-administer starting from Week 6. At Weeks 12, 24, 32, 36, 3 to 5 days prior to Week 48 Visit and Week 48 in Period 2, subjects will visit the site and undergo relevant tests and assessments according to [Table 5.1](#). The injection schedule ([Figure 7.1](#)) will provide the sequence of self-administration and site visits including administration at the site.

All subjects who have not achieved sustained remission at the end of Period 2 (Week 48) will be discontinued from the study and treated at the discretion of their physician. Those subjects who discontinue prematurely from the study for any reason will be treated at the discretion of their physician.

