Abs=antibodies; ADAb= anti-CZP antibody; AEs=adverse events; AS=ankylosing spondylitis; AsQoL=Ankylosing Spondylitis Quality of Life; axSpA=axial spondyloarthritis; BASDAI=Bath Ankylosing Spondylitis Disease Activity Index; BASFI=Bath Ankylosing Spondylitis Functional Index; BASMI=Bath Ankylosing Spondylitis Metrology Index; CRP=C-reactive protein; CZP=certolizumab pegol; EQ-5D=EuroQoL Health Status Questionnaire; H=home, no site visit; HIV=human immunodeficiency virus; HLA-B27=human leukocyte antigen B27; HN=home nurse visit at subject's home; IBD=Inflammatory bowel disease; incl.=including; inj= injection; IXRS=Interactive Voice or Web Response System; MASES=Maastricht Ankylosis Spondylitis Enthesitis Score; MRI=magnetic resonance imaging; PE=physical exam; sc=subcutaneously; SF-36=Short-Form 36-item Health Survey; SFU=Safety Follow-Up; SI=sacroiliac; subj=subject; TB=tuberculosis; W=Week; WD=Withdrawal; WHO=World Health Organization

^a Assessments conducted 3 to 5 days prior to Week 48 will serve as the qualification assessments for subjects determined to be eligible for randomization into Part B at Week 48.

^b SFU: 10 weeks after last dose of study medication.

^c Informed consent: Prior to any study activities, subjects will be asked to read and sign the informed consent form for the conduct of the study. A separate informed consent form will be obtained from subjects consenting also to the use of their blood samples for possible genetic, genomic, and proteomic analysis.

^d Pulse rate, systolic and diastolic blood pressures, temperature, and respiration rate are to be measured at Screening and Baseline, thereafter pulse rate, systolic and diastolic blood pressures and temperature are to be measured. If a subject experiences an AE, respiration rate will be measured in addition.

^e Testing to rule out hepatitis B surface antigen, antibodies to hepatitis C, antibodies to HIV and HLA-B27 at Screening only.

^f To be assessed as indicated and from Week 52 onwards every 4 weeks only.

^g Pregnancy testing for women of childbearing potential will be serum testing at the Screening Visit and SFU and urine testing at Baseline and Week 96/WD Visit.

^h Includes evaluation of signs and symptoms of active TB and risk factors for exposure to TB. Weight is to be measured at Screening, Baseline, Week 48, and at Week 96/WD. Height will be measured at the Baseline Visit only.

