ⁱ Screening chest x-ray must have occurred within 3 months prior to Screening or during Screening, and should be repeated only if the TB test was confirmed positive or any further evidence is suggestive of potential TB infection (eg, exposure).

^j QuantiFERON TB GOLD test or another WHO-validated IGRA test such as Elispot test, if QuantiFERON TB GOLD test is not locally available. The TB test will be repeated at Week 48 and 96 (or at WD Visit if medically indicated) for subjects with previously negative TB test result.

^k Sacroiliac joint x-rays will be performed at Screening and used as the Baseline assessment for all subjects. An SIJ x-ray performed \leq 12 months prior to the Baseline Visit may be used as the Baseline assessment provided that the film can be submitted and meets the requirements for central reading.

^l Magnetic resonance imaging of the spine and sacroiliac joints to be performed at Screening, and within a \pm 2 weeks time window at Weeks 48 and 96 or WD Visit if the last MRI was performed more than 12 weeks prior to WD Visit.

^m Kit for collection of stool sample to be provided at Screening Visit. Stool sample shall be obtained prior to Baseline and provided to the Investigator at the Baseline Visit.

ⁿ Occiput to wall distance; chest expansion; and BASMI, which includes modified Schober test, lateral spinal flexion, cervical rotation, tragus to wall distance, and maximal intermalleolar distance.

^o Resource utilization includes: concomitant medical procedures, health care provider consultations not foreseen by the protocol, hospitalizations/emergency room visits.

^p Prior medication will be at Screening only.

^q Nurse visit at home only where approved and with agreement of subjects. Otherwise, the visit procedures will be done onsite by the site staff.

^r Refer to Protocol [Section 3](#) for definition. In case of loss of sustained remission in Part B, the subject must visit the study site for the next scheduled dose of study medication. The Investigator will initiate the escape treatment as appropriate. Refer to [Table 5.2](#) for details.

^s Subjects will be contacted by telephone about every 4 weeks in between the onsite visits.

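### The Week 48 IGRA is drawn at the visit where subjects are randomized and dosed; drawing it at the existing visit 3 to 5 days earlier would give the TB stop rules a chance to act first

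*Protocol*

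**What the plan says.** The repeat IGRA is placed at Week 48 and Week 96 throughout. Section 8.3.1 has "TB test (at Week 48 and at Week 96/WD only", and Table 5.1 footnote j has "The TB test will be repeated at Week 48 and 96"; Sections 4.4 and 12.7.3.1 agree. Week 48 is therefore the only scheduled IGRA between Screening and Part B.

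Section 8.3.1 also has "Randomization at Week 48", and study drug given "after all other visit assessments are completed and laboratory samples are drawn".

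Before that comes a separate visit. Section 5.1.1 states: "3 to 5 days prior to Week 48 Visit and Week 48 in Period 2, subjects will visit the site". Table 5.1 footnote a gives its purpose: "Assessments conducted 3 to 5 days prior to Week 48 will serve as the qualification assessments". Section 8.3.2 lists its content, starting with "Blood samples will be collected for hematology and biochemistry analyses and CRP" and going on to plasma, genetic and serum calprotectin samples. No TB test is on that list.

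The entry condition in Section 3 is "A subject is eligible for Part B of the study only if sustained remission is achieved in Part A".

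The TB rules act on results. Under Section 12.7.3, a subject whose IGRA turns positive stops study drug at once and is referred. If latent TB is found, dosing may resume at the earliest 4 weeks after prophylaxis starts; without prophylaxis the subject is withdrawn. Section 12.7.3.1 bars continued treatment after a positive or repeat-indeterminate result until a TB specialist has evaluated the subject, and requires results to be reviewed by a TB specialist, radiologist or pulmonologist.

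**The concern.** The stop rules cannot act on a sample taken shortly before the injection at the same visit. Nothing in the current text requires the Week 48 result before randomization or before the Week 48 dose.

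The TB questionnaire and physical examination are also done at Week 48 and can pick up symptomatic or exposed subjects. The gap is the asymptomatic converter with no reported exposure. That subject is randomized, receives at least one further administration, and then faces the interruption of at least 4 weeks, or withdrawal.

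What is at stake is patient safety on a small scale: an avoidable anti-TNF dose in someone with a new positive TB test. The sample could have been taken a few days sooner at a visit that already draws blood.

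**Working it through.** The plan gives no figure on this point, so the check counts administrations given before the result is known.

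**Inputs**
- Week 48 dose = day 0, Week 50 dose = day 14, then every 14 days (Table 5.1).
- Draw day D = 0 as written; D = −3 or −5 at the qualification visit (Section 8.3.2).
- T = days from draw to a reviewed result. **Assumption**: not in the protocol, so a range is shown. It must include the review required by Section 12.7.3.1. A result available on the dosing day counts as in time.

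**Rule**: a dose on day d is given before the result is known if d < D + T.

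| Administrations before the result | D = 0 (as written) | D = −3 | D = −5 |
|---|---|---|---|
| 0 | T = 0 | T = 0 to 3 | T = 0 to 5 |
| 1 | T = 1 to 14 | T = 4 to 17 | T = 6 to 19 |
| 2 | T = 15 to 28 | T = 18 to 28 | T = 20 to 28 |

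**Effect of moving the draw**
- T = 0: none.
- T = 1 to 3 (D = −3) or 1 to 5 (D = −5): the Week 48 administration and the randomization of a known converter are avoided.
- Longer T: the Week 48 dose is given as now and the result arrives 3 to 5 days sooner. That changes the dose count again only at T = 15 to 17 or 15 to 19, where it precedes the Week 50 dose.
- At no T is the earlier draw worse.

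**Scale**
- Doses already received in Part A: Weeks 0, 2, …, 46 = 46/2 + 1 = 24 occasions.
- The conversion rate c is also not in the protocol. At an assumed 1% to 5%, 210 × c = 2.1 to 10.5 randomized subjects and 70 × c = 0.7 to 3.5 in the full-dose arm. These are upper counts, because the questionnaire and examination catch some.

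**Cost in sample size, as a bound**
- Section 14.8 states 98% and 94% power with 70 per group (80% and 75% against 45% flare-free, 2-sided 0.05). The normal approximation with pooled null variance and continuity correction 1/n is Φ[(Δ − 1/n − 1.96·SE₀)/SE₁].
- Full-dose, n = 70: Δ = 0.35, SE₀ = 0.0818, SE₁ = 0.0763, power 98.9%. Half-dose: Δ = 0.30, SE₀ = 0.0828, SE₁ = 0.0788, power 94.1%. Both agree with the plan to within a point.
- Suppose every converter were caught, not randomized and not replaced. Then 70 × (1 − c) leaves 69 (c = 1%) or 66 (c = 5%) per arm, with power 98.8% or 98.5% (full-dose) and 93.8% or 92.6% (half-dose).

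**The case against.** The strongest objection is that the benefit hangs on a turnaround the protocol does not give. The test may be run locally, and IGRA is not among the central laboratory analytes in Table 12.2. The specialist review must also fit into the 3 to 5 days, and an indeterminate result needs a second cycle. The period in which a dose is actually avoided is therefore narrow. The subject has had 24 dosing occasions already, the placebo arm gets no CZP, and latent TB without prophylaxis was excluded at Screening. All of this stands, and it limits the point to a modest gain.

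Several stronger readings are tempting, but the documents do not support them:

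- **That the protocol breaks its own TB rule.** Section 12.7.3 says that a positive or repeat-indeterminate subject may not be randomized without evaluation, but that paragraph ties the retest to the Screening window. The rules for later tests act on results. No rule is broken.
- **That remission is the sole gate to Part B.** Section 3 makes it necessary, not exclusive, and Section 12.7.3.1 separately restricts treatment after a positive test.
- **That Section 8.1 shows the opposite principle by recommending the IGRA first at Screening.** Its stated reason is to spare screening procedures. It says nothing about timing a repeat test relative to dosing.
- **That randomization should be held, or the +3-day visit window used, until the result is in.** This would age the qualifying data beyond the 3 to 5 days before the Week 48 visit on which Table 5.1 and Section 14.2 rely. A longer hold would also need a requalification rule that the protocol does not have.

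**Conclusion.** The point holds as a sequencing weakness with a nearly free remedy. With the draw at Week 48, any turnaround of 1 to 14 days means that an asymptomatic converter with no reported exposure is randomized and receives one further administration; at 15 to 28 days it is two. An earlier draw prevents the Week 48 dose only if the reviewed result is back within 3 to 5 days. Otherwise the site simply learns the result 3 to 5 days sooner.

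This rests on two quantities that the protocol does not give: turnaround and conversion rate. The dose at issue is CZP in the full-dose arm and none in the placebo arm. For the half-dose arm it depends on Figure 7.1, which is not shown.

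A reader might infer a gain in bias, power or the quality of the Randomized Set. None is claimed: the numbers are too small and the benefit too conditional. The case is one of patient safety at negligible cost.

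**What to change.** Move the Week 48 IGRA draw to the visit 3 to 5 days before Week 48. Amend Sections 8.3.1, 8.3.2, 4.4 and 12.7.3.1, and Table 5.1 with footnote j. Have the site check any available result before contacting the IXRS to randomize:

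- **Known negative:** randomize and dose as planned.
- **Known positive or repeat-indeterminate:** do not randomize or dose until evaluated under Section 12.7.3.
- **Pending at Week 48, including a pending retest:** proceed as now under the existing stop rules, with no use of the +3-day window, no hold and no new re-entry rule.

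The TB stopping and treatment rules stay as they are.

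The cost is one tube taken at a visit that already draws blood, in the same subjects, with no added test, visit or staff. In the Section 8.3.1 list the IGRA is the only blood sample at Week 48, so the move may save a venipuncture there. A few converters may not be randomized; the bound above shows that this barely affects power, and Section 14.8 already provides for adapting enrollment to reach 210.

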8.4 Weeks 6 to 94 home visits and home nurse visits

8.4.1 Home visits during Part A

Assessments at these home visits include:

- Study drug self-administration at home (at Weeks 6, 8, 10, 14, 16, 18, 20, 22, 26, 28, 30, 34, 38, 40, 42, 44, and 46)
- Subjects will be contacted by telephone in between the onsite visits (at Weeks 6 to 10, 14 to 22, 26 to 30, and 38 to 46)

8.4.2 Home and home nurse visits during Part B

Assessments at these home and nurse visits include:

- Vital signs: pulse rate, systolic and diastolic blood pressures, temperature will be measured. If a subject experiences an AE, respiration rate will be measured in addition (at Week 50, Weeks 54 to 58, 62 to 70, 74 to 82, and 86 to 94 only)

- CRP and PtGADA (at Weeks 50, 56, 64, 68, 76, 80, 88, and 92)
- BASDAI (at Weeks 50, 56, 64, 68, 76, 80, 88, and 92)
- Contact IXRS to report kit number (all Visit at Weeks 50, 54 to 58, 62 to 70, 74 to 82, and 86 to 94)
- Nurse visit at subject home including to perform study medication administration (at Weeks 50, 54, 56, 58, 62, 64, 66, 68, 70, 74, 76, 78, 80, 82, 86, 88, 90, 92, and 94)
- Check of sustained remission criteria (at Weeks 50, 56, 64, 68, 76, 80, 88, and 92)

8.5 Study procedures after flare until the final assessment visit at Week 96/WD

The assessment schedule for subjects experiencing a flare in Part B will start 2 weeks after the flare condition is fulfilled (Escape Week 0) and will end 2 weeks before the final assessment visit at Week 96 (whereas the appointment for Week 96 is to be scheduled in accordance to the regular assessment schedule [Table 5.1] with Week 0 as Baseline). If the flare occurs late in Part B (at or after Week 82), the subject must receive the escape treatment for 12 weeks (eg, starting at Week 84 [Escape Week 0] until Week 96 [Escape Week 12]). The final assessments at study end (as laid down for Week 96 of the regular schedule) must be performed 2 weeks after the last study dose administration accordingly (ie, 98 weeks after Baseline for the example provided).

Assessments and their timing after a flare are specified in Table 5.2 and include:

- Vital signs: pulse rate, systolic and diastolic blood pressures, temperature will be measured at Escape Weeks 0, 2, 4, 12, and every 12 weeks thereafter until the final assessment visit at Week 96/WD. If a subject experiences an AE, respiration rate will be measured in addition
- Blood samples will be collected for hematology and biochemistry analyses at Escape Week 0 and every 12 weeks thereafter until the final assessment visit at Week 96/WD
- Urine will be collected for urinalysis at Escape Week 0 and every 12 weeks thereafter until the final assessment visit at Week 96/WD
- CRP at Escape Weeks 0, 2, 4, and every 4 weeks thereafter until the final assessment visit at Week 96/WD
- MRI at Escape Weeks 0 and 12, and at final assessment visit at Week 96/WD, if the last MRI was done at least 12 weeks prior to Week 96/WD
- Stool sample will be collected for fecal calprotectin and blood sample for serum calprotectin at Escape Weeks 0 and 12
- IBD-Q at Escape Weeks 0 and 12
- Physical examination at Escape Weeks 0, 2, 4, 12, and every 12 weeks thereafter until the final assessment visit at Week 96/WD
- Extra-articular assessments at Escape Weeks 0, 4, 12, and every 12 weeks thereafter until the final assessment visit at Week 96/WD

- TB questionnaire at Escape Week 0 and every 12 weeks thereafter until the final assessment visit at Week 96/WD
- BASMI and spinal mobility at Escape Weeks 0, 2, 4, 12, and every 12 weeks thereafter until the final assessment visit at Week 96/WD
- BASDAI at Escape Weeks 0, 2, 4, and every 4 weeks thereafter until the final assessment visit at Week 96/WD
- BASFI at Escape Weeks 0, 2, 4, 12, and every 12 weeks thereafter until the final assessment visit at Week 96/WD
- SF-36 at Escape Weeks 0, 4, 12, and every 12 weeks thereafter until the final assessment visit at Week 96/WD
- ASQoL at Escape Weeks 0, 2, 4, 12, and every 12 weeks thereafter until the final assessment visit at Week 96/WD
- EQ-5D at Escape Weeks 0, 4, 12, and every 12 weeks thereafter until the final assessment visit at Week 96/WD
- MASES at Escape Weeks 0, 2, 4, 12, and every 12 weeks thereafter until the final assessment visit at Week 96/WD.
- Total spinal pain NRS and nocturnal spinal pain NRS at Escape Weeks 0, 2, 4, 12, and every 12 weeks thereafter until the final assessment visit at Week 96/WD
- PtGADA at Escape Weeks 0, 2, 4, and every 4 weeks thereafter until the final assessment visit at Week 96/WD
- PhGADA at Escape Weeks 0, 2, 4, 12, and every 12 weeks thereafter until the final assessment visit at Week 96/WD
- WPS at Escape Weeks 0, 4, 12, and every 12 weeks thereafter until the final assessment visit at Week 96/WD
- Resource utilization at Escape Weeks 0, 4, 12, and every 12 weeks thereafter until the final assessment visit at Week 96/WD
- Plasma for CZP concentration and ADAbs at Escape Weeks 0, 2, 4, 12, and every 12 weeks thereafter until the final assessment visit at Week 96/WD
- Plasma for biomarkers at Escape Weeks 0, 2, 4, 12, and every 12 weeks thereafter until the final assessment visit at Week 96/WD, if applicable.
- Concomitant medication at Escape Weeks 0, 2, 4, 12, and every 12 weeks thereafter until the final assessment visit at Week 96/WD
- AEs
- Contact IXRS to obtain next kit numbers
- Study drug administration (after all other visit assessments are completed and laboratory samples are drawn) at site and study drug self-injection at home

Refer to [Table 5.1](#) and [Section 8.3](#) for the final assessments due at Week 96/WD.

